### ***Quality of Health Survey (Mental and Physical Health – SF-12)***

A modified version of the SF-12 outcome measure was used. The SF-12 is a validated, health-related quality of life (HRQoL) survey. The SF-12 is designed to be able to measure physical and mental health. We modified the format of the original SF-12 survey to fit our population. Modifications to the survey included reformatting of the item and response presentations, using a larger font size. Permission to use the survey items in our study was granted by OPTUM.

The survey instrument was pre-tested for face validity by administration to 102 Medicare patients with chronic low back pain, over the age of 65, who had received at least two chiropractic spinal manipulation treatments for their low back pain at the Southern California University of Health Sciences' University Health Center. After examining the face validity of the survey, and based on feedback, for ease of comprehension by older subjects, the survey questions were printed in larger font and carefully worded to be brief, unambiguous, and free from bias.

## **Data Analysis**

We generated descriptive statistics including computation of means for continuous variables and percentages for categorical data. We examined between-group differences for our three measures. Specifically, we first compared outcomes for the SMT and OAT cohorts to test our primary hypotheses and subsequently compared outcomes for the SMTX and OATX cohorts as exploratory analyses.

In order to address our primary hypothesis, we collapsed the response options as follows: response options for satisfaction with care items, 8-10, we coded as 'Very satisfied' and response options <8, we coded as 'Less satisfied'. We conducted Pearson chi-square tests to examine differences between groups for the Beliefs about Treatment items as well as for the overall satisfaction with treatment items.

Additionally, for the Beliefs about Treatment items, we combined the response options using the following categories: Disagree (combined Strongly disagree with Disagree), Agree (combined Strongly agree with Agree), Undecided was left as is. Group mean differences for the SF-12 mental and physical health scores were examined using *t*-tests. We performed *t*-tests for group mean comparisons utilizing the entire 0-10 scale for overall satisfaction as well. Additionally, we conducted the Kruskal-Wallis non-parametric test to accommodate non-normality in the distribution of the data for the Beliefs about Treatment items. All analyses were conducted using IBM SPSS (Version 23).

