### **Cohort Definitions**

All included patients received long term management of cLBP with SMT or OAT. SMT was identified in clinical claims data by Current Procedural Terminology (CPT) code 98940, 98941, or 98942. OAT was identified as opioid analgesics or analgesics containing opioids, identified by drug code and obtained by prescription through an outpatient pharmacy. For OAT, we defined long-term management as 6 or more standard 30-day supply prescription fills in a 12-month period. For SMT, we defined long-term management as  $\geq 12$  office visits for spinal manipulation for LBP in any 12-month period, including at least one visit per month. We assembled two primary and two crossover cohorts as follows:

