#### **Primary Cohorts**

SMT= Initiation in 2013 of long-term management with SMT, and no OAT for 12 months after initiating SMT

OAT = Initiation in 2013 of long-term management with OAT, and no SMT for 12 months after initiating OAT

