## **Survey Procedures**

Following cohort assembly, potential survey participants were selected by random sampling of subjects in each of the four cohorts. The list of potential survey participants was securely transmitted to the Centers for Medicare and Medicaid Services (CMS), and initial contact was made by CMS in the form of a Beneficiary Notification Letter, signed by the CMS Privacy Officer. This letter notified the selected Medicare beneficiaries of the opportunity to participate in a healthcare survey, and allowed them the option to decline participation via enclosed reply forms. Upon conclusion of this process, CMS provided us with contact information for beneficiaries that had been determined to be eligible for voluntary participation in the survey. CMS provided contact information for 2,490 participants; beneficiaries who were deceased or without contact information were removed. A total of 1,986 surveys were hand-addressed and mailed to the Medicare beneficiaries on 01/10/2020. All available phone numbers were used to make reminder phone calls and two weeks after initial mailing, 1,070 reminder surveys were re-sent to cohorts with lower response rates. The data was entered into an MS Excel spreadsheet, with double data entry and data verification. Patient's signed consent was obtained prior to participate in the study.

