## **Outcome Measures**

### ***Overall Satisfaction with SMT and PDT***

The survey measured satisfaction for both SMT and PDT on a scale from 0-10, 0 being very dissatisfied and 10 being very satisfied. The patients were also given an option to select 'not applicable' if they never experienced either PDT or SMT. Literature indicates that for quantifying satisfaction among patients, Numeric Rating Scales can be used.

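### Cohorts defined by treatment received are compared only with unadjusted tests, so any treatment-related reading of SMT versus OAT differences may reflect patient mix

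*Combined protocol and SAP*

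**What the plan says.** Cohort Definitions in the combined protocol and SAP states: "All included patients received long term management of cLBP with SMT or OAT". Primary Cohorts then sets out two groups according to which treatment was used: "OAT = Initiation in 2013 of long-term management with OAT, and no SMT for 12 months after initiating OAT", with the SMT cohort as its mirror image. Membership is read from claims, and nobody was allocated. The one random step is in Survey Procedures: "potential survey participants were selected by random sampling of subjects in each of the four cohorts".

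Data Analysis says that "we first compared outcomes for the SMT and OAT cohorts to test our primary hypotheses". The tests are these:

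- Pearson chi-square: "We conducted Pearson chi-square tests to examine differences between groups for the Beliefs about Treatment items as well as for the overall satisfaction" items, with satisfaction split at 8-10 versus below 8.
- t-tests: "Group mean differences for the SF-12 mental and physical health scores were examined using" t-tests, which are also applied to the full 0-10 satisfaction scale.
- Kruskal-Wallis tests on the belief items.

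The sections from Methods to Data Analysis describe no regression, covariate, matching, weighting or stratified analysis. The only control is the set of eligibility rules common to both cohorts (Population). Satisfaction is two items: "The survey measured satisfaction for both SMT and PDT on a scale from 0-10". For these, "The patients were also given an option to select 'not applicable' if they never experienced either PDT or SMT".

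**The concern.** Random sampling within a cohort makes the sample represent that cohort. It does nothing to make SMT patients resemble OAT patients. Shared eligibility narrows the differences, but it still spans ages 65 to 84 and, among health conditions, removes only cancer and hospice use. Other illness, earlier hospital use and pain severity may differ between people on long-term opioids and people attending regular manipulation.

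The SF-12 scores are the most exposed. They measure general physical and mental health, and no pre-treatment measurement is described. Episodes began in 2013 and the survey was mailed on 01/10/2020, about six to seven years after the index visit. A difference in SF-12 could be the difference in health that led to the choice of treatment.

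More respondents would not help. The shift due to patient mix does not depend on sample size, so a larger survey only makes it more likely to reach significance.

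**Working it through.** The plan gives no target difference, rate, standard deviation, alpha or respondent number, so there is no figure to reproduce. What follows is an illustration of scale. **All inputs are assumptions**: no treatment effect, one binary patient factor, 60% very satisfied without the factor, and 150 respondents per cohort. For context, 1,986 / 4 = 496.5 surveys per cohort if the mailing was evenly split (not stated), so 150 would be about 30% response.

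**1. Shift in the crude difference.** With factor prevalence a in SMT and b in OAT, shift = (b − a) × (0.60 − p1), where p1 has odds 1.5 × OR.

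- OR 0.67: p1 = 1.005/2.005 = 0.5012
- OR 0.5: p1 = 0.75/1.75 = 0.4286
- OR 0.33: p1 = 0.495/1.495 = 0.3311

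For the 35/65 case, 0.30 × 0.1714 = 0.0514; that is, 54.0% against 48.9%.

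**2. Rejection rate of the nominal 5% test.** Crude rates are for the Pearson chi-square by exact binomial enumeration. Adjusted rates are for a logistic Wald test with the factor as covariate, from 20,000 simulations per setting.

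| Prevalence SMT/OAT, OR | Shift (points) | Crude | Adjusted, factor exact | Adjusted, factor 75% accurate |
|---|---|---|---|---|
| 45/55, 0.67 | 0.99 | 5.9% | 5.2% | 5.6% |
| 40/60, 0.67 | 1.98 | 7.0% | 5.2% | 6.1% |
| 35/65, 0.5 | 5.14 | 15.7% | 5.2% | 10.5% |
| 30/70, 0.33 | 10.76 | 48.4% | 4.8% | 30.2% |

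**3. Sample size.** In the 35/65 case the simulated crude rate is 10.6%, 15.8% and 24.7% at 75, 150 and 300 per cohort. The shift stays at 5.14 points throughout.

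**4. t-tests (SF-12, 0-10 satisfaction).** Bias in SD units = imbalance × effect, and SE = √(2/150) = 0.1155.

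- 0.10 × 0.2 = 0.02 SD: z = 0.17, rejection 5.3%
- 0.30 × 0.5 = 0.15 SD: z = 1.30, rejection 25.5%
- 0.40 × 0.8 = 0.32 SD: z = 2.77, rejection 79.1%

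**5. Covariates unrelated to the factor.** If the adjustment variable carries no information on the factor, logistic adjustment still rejects roughly 13 to 15% of the time in the 35/65 case and 46% in the 30/70 case, close to the crude rates.

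**6. Price in precision.** The SE inflates by 1/√(1 − φ²), where φ is the correlation between covariate and cohort. With equal cohorts, φ = 0.3 for a 35/65 split, giving 1.05. For 20/80 (φ = 0.6) it is 1.25, and for 10/90 (φ = 0.8) it is 1.67.

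**The case against.** The strongest reply is that the study may make no claim about treatment effects. The wording of the hypotheses lies in text removed before review. What can be seen is a survey that compares groups. If the null is that the two populations do not differ, the rates above are power to detect a real difference and not false positives. **This stands.** A reader might infer that the crude tests are invalid or the results biased, but the documents support neither: the tests are sound as descriptions, and the imbalance is unknown.

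A second objection is that adjustment may achieve little. Linkage of survey responses to claims covariates is not described. Reminders went to cohorts with lower response, which shows that the cohort label was tracked but nothing more. If age and sex are unrelated to the real confounders, step 5 shows that adjusting for them removes almost nothing. **This stands too.** A reader might infer that adjusted results would justify a treatment conclusion. They would not, and treating them so would give false assurance.

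Third, for beliefs the order of events is unclear. Beliefs measured in 2020 may have led to the treatment choice or followed from it, and a comorbidity score does not resolve that.

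Finally, it is tempting to argue that each cohort's ratings of the other treatment come from a selected few, because the other treatment was excluded for 12 months. This is weak for the drug item. It asks about prescription drug therapy (PDT), which the documents do not limit to opioids, and the opt-out is for those who never had the treatment. Having no OAT for 12 months does not show that the SMT cohort had no PDT.

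**Conclusion.** The point holds in conditional form. It is certain that the cohorts follow treatment received and that no test named in Data Analysis is adjusted. It follows that any treatment-related reading of an SMT versus OAT difference cannot be separated from patient mix on the planned analysis.

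The size is not known. Under the assumed inputs it runs from close to nil (a 1-point shift, 6% rejection) to large (an 11-point shift, 48% rejection). Those rates count as false positives only if the hypothesis is about treatment. If the hypotheses are descriptive, the crude analysis stands and only the interpretation needs the caveat. The change is worth making because it needs no new patients and would show whether the differences survive adjustment for measured characteristics.

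**What to change.** Keep the crude tests, labelled as descriptions. Beside them:

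- Report SMT versus OAT adjusted for age, sex and a short list of claims variables from before the index visit, such as a comorbidity score and prior hospital use, where responses can be linked to claims. Enrolment in Parts A, B and D from 2012 provides a period before the 2013 episodes. If linkage is not possible, adjust for age and sex and say that this may control little.
- Use logistic regression for satisfaction 8-10 versus below 8, and linear regression for 0-10 satisfaction and the SF-12 physical and mental scores. Treat multinomial models for the belief items as secondary.
- Analyse the SMT and PDT satisfaction items separately, and report the number answering not applicable in each cohort.
- Describe every difference, crude or adjusted, as an association and draw no treatment-effect conclusion from either. Give the reasons: pain severity and prior beliefs are unmeasured, no baseline SF-12 is described, and the survey came about six to seven years after the index visit.

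The cost is some extra analysis and wording. Standard errors widen by about 5% for a covariate split 35/65 and by much more for one that nearly identifies the cohort, so the list should stay short. The claims-based version depends on linkage that the documents do not describe, and unmeasured confounding remains in either version.

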### ***Beliefs about Treatments Received***

This study included an 8-item assessment of participant beliefs regarding their treatment of SMT and PDT. These survey items were taken from a validated scale (patient's treatment belief low back pain questionnaire) developed by Dima et al., with permissions from the author(s). A modified version of LBP treatment belief questionnaire scale (LBP TBQ Scale) was used for this study. An example of a belief question was: "I think spinal manipulation is pretty useless for people with back pain," or "I believe Prescription Drug therapy (PDT) is pretty useless for people with back pain." Responses ranged from Strongly Disagree, Disagree, Agree, Strongly Agree and Undecided in a 5-point Likert scale. For purposes of analysis, we combined the response options into the following three categories: "Disagree" (Strongly Disagree and Disagree), "Agree" (Strongly Agree and Agree), and "Undecided"(left as is).

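### Does the unstated rank of Undecided undermine the Kruskal-Wallis test on the belief items?

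*Combined protocol and SAP*

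**What the plan says.** Under Beliefs about Treatments Received, the answer options are introduced this way: "Responses ranged from Strongly Disagree, Disagree, Agree, Strongly Agree and Undecided in a 5-point Likert scale". The same section then says: "For purposes of analysis, we combined the response options into the following three categories". The Data Analysis section repeats the grouping as "Disagree (combined Strongly disagree with Disagree), Agree (combined Strongly agree with Agree), Undecided was left as is".

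Two tests are named for these items. The first is the chi-square: "We conducted Pearson chi-square tests to examine differences between groups for the Beliefs about Treatment items". The second, added at the end of the section, is the rank test: "we conducted the Kruskal-Wallis non-parametric test to accommodate non-normality in the distribution of the data for the Beliefs about Treatment items". Descriptive output is also planned: "We generated descriptive statistics including computation of means for continuous variables and percentages for categorical data".

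Cohorts are compared two at a time: SMT with OAT for the primary hypotheses, then SMTX with OATX as exploratory work. Neither section gives numeric codes or a rank for Undecided. The grouping into three categories is stated for analysis in general and is not tied to the rank test by name.

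**The concern.** A Kruskal-Wallis test means nothing until the categories are put in order. If the order of the prose list became the coding, an undecided respondent would rank above one who strongly agrees, and the test would mix willingness to give an opinion with the opinion itself. Three things could then go wrong:

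- a small p-value could come only from different Undecided shares;
- a real shift in agreement could be cancelled and missed;
- mean ranks, if read, could point the wrong way.

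The stated reason for the test does not help. Non-normality says nothing about order, and the chi-square on the same items never assumed normality.

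**Working it through.** **Inputs.** The plan has no figure to reproduce: it states no response shares, respondent counts or significance level for this test. The one usable number is in Survey Procedures: "A total of 1,986 surveys were hand-addressed and mailed to the Medicare beneficiaries on 01/10/2020". Split equally over four cohorts, that is 1,986/4 = 496.5 mailed per cohort. The assumed 200 respondents per cohort is therefore a response of 200/496.5 = 40%. All shares below are assumed, and 0.05 is used as a conventional threshold.

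**Formulas.** With two cohorts of 200, N = 400 and the average rank is 200.5. Let d be the distance of each cohort's mean rank from 200.5.

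- H = [12/(N(N+1))] × 2 × 200 × d² / C = (4,800/160,400) × d² / C, on 1 df
- C = 1 − Σ(t³ − t)/(N³ − N), where t runs over the category totals
- Chi-square on the 2×3 table: Σ(O − E)²/E, on 2 df, with p = exp(−χ²/2)

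**One case in full.** Table (a) has counts (Disagree, Agree, Undecided) of 80, 80, 40 against 60, 60, 80, so the totals are 140, 140, 120.

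- *Undecided last.* Midranks are 70.5, 210.5 and 340.5. The first cohort's mean rank is (80×70.5 + 80×210.5 + 40×340.5)/200 = 180.5, so d = 20. C = 1 − 7,215,600/63,999,600 = 0.8873. H = 11.97/0.8873 = 13.49, p = 0.0002.
- *Undecided in the middle.* Midranks are 70.5 (Disagree), 200.5 (Undecided) and 330.5 (Agree). The mean rank is (80×70.5 + 40×200.5 + 80×330.5)/200 = 200.5, so d = 0, H = 0 and p = 1.0.
- *Chi-square.* 4×10²/70 + 2×20²/60 = 19.05, p = 0.00007, whatever the order.

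**All tables, three levels, 200 per cohort.**

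| Disagree/Agree/Undecided % | Undecided ranked | Mean ranks | d | C | H | p | Chi-square (p) |
|---|---|---|---|---|---|---|---|
| (a) 40/40/20 v 30/30/40 | last | 180.5 v 220.5 | 20 | 0.8873 | 13.49 | 0.0002 | 19.05 (0.00007) |
| (a) | middle | 200.5 v 200.5 | 0 | 0.8873 | 0 | 1.0 | same |
| (b) 20/60/20 v 20/40/40 | last | 184.5 v 216.5 | 16 | 0.8400 | 9.12 | 0.0025 | 21.33 (0.00002) |
| (b) | middle | 216.5 v 184.5 | 16 | 0.8400 | 9.12 | 0.0025 | same |
| (c) 20/70/10 v 30/40/30 | last | 193.5 v 207.5 | 7 | 0.8100 | 1.81 | 0.18 | 40.36 (0.000000002) |
| (c) | middle | 227.5 v 173.5 | 27 | 0.8100 | 26.93 | 0.0000002 | same |
| (d) 40/40/20 v 37.5/37.5/25 | last | 195.5 v 205.5 | 5 | 0.8722 | 0.86 | 0.35 | 1.43 (0.49) |
| (e) 40/40/20 v 35/35/30 | last | 190.5 v 210.5 | 10 | 0.8789 | 3.40 | 0.065 | 5.33 (0.07) |

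The dependence on coding is therefore real, but tables (a) to (c) all use a 20-point gap in Undecided. With an even agree:disagree split and Undecided last, the p-value at expected counts first falls below 0.05 at 58 per cohort for a 20-point gap, 226 for a 10-point gap and 895 for a 5-point gap. The last exceeds the roughly 497 mailed per cohort under an equal split.

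**What the text supports.** Naming the two disagreeing and two agreeing options together and then the remaining one is an ordinary way to write a list. It is weak evidence for codes. Describing the options as a 5-point Likert scale points to an ordered scale, on which Undecided would normally sit in the centre. On the number of levels, the general statement that responses were grouped for analysis makes three the natural reading, and the ordering question is the same with three or five.

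**The case for a change.** The best case for acting is that the text allows two codings that can give opposite readings, that the team chose to run this test on eight items in two cohort comparisons, and that one sentence would settle the matter. It can be added that the chi-square carries no direction along an agreement scale, so it does not replace a correctly ordered rank test.

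Part of this stands. The codes are missing, and a reader given only a Kruskal-Wallis p-value could not tell what was compared.

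The rest does not lead to a change. The stated aim is to find differences between cohorts, and in table (a) the two distributions do differ, so a small p-value there is not a false positive against that aim. Not knowing whether a small p-value reflects agreement or the Undecided share applies equally to the chi-square, and the planned percentages resolve it for both. They also show direction. The alternatives carry assumptions of their own: a middle position for Undecided is itself a choice, and dropping undecided respondents makes the groups compared depend on the answer given.

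**Conclusion.** The concern does not hold as a fault in the plan. It identifies a detail that an analyst fills sensibly when coding an agreement scale, and nothing in the documents shows that it was filled wrongly. The harm arises only if Undecided was coded last and its share differs widely between cohorts. A 20-point gap would matter even at 100 per cohort (p = 0.009 last against 1.0 in the middle for the shares in table (a)), a 10-point gap mainly in larger cohorts, and a 5-point gap hardly at all. Those sizes rest on assumed shares, equal cohorts and, for the gap comparison, an even agree:disagree split.

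Even in the worst case the damage is confined to a supplementary test. The chi-square is named first, does not use order, and gives p below 0.01 in tables (a) to (c) at both 100 and 200 per cohort. No conclusion is made to depend on the rank test. Naming the codes beside any reported Kruskal-Wallis result would be good reporting, but the planned analysis does not need to change.
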